10.3.4 Handling of patients after permanent treatment discontinuation

Patients will be followed-up according to the study procedures as specified in this protocol up to the scheduled date of study completion, or up to recovery or stabilization of any AE to be followed-up as specified in this protocol, whichever comes last. Study Investigators should continue background therapy after treatment discontinuation, as guided by their medical judgement.

Patients who prematurely discontinue the study medication, at the time of permanent treatment discontinuation, patients will perform:

- Early EOT visit: 2 weeks (with a ± 3 days window) after last IMP injection. If the time of decision taken for permanent IMP discontinuation is >2 weeks $+3$ days after last IMP injection, this early EOT visit should be scheduled as early as possible from permanent discontinuation of IMP decision. All the assessments defined for the EOT Visit 10 will be performed during this early EOT,
- Early EOS visit: 12 weeks after early EOT visit with a ± 1 week window. All the assessment defined for the EOS Visit 11 will be performed during this visit.

Patients who discontinue early from treatment may be asked to return to the clinic to have additional ADA samples collected for analysis based on the overall assessment of antibody titers and clinical presentation at the time of discontinuation.

All cases of permanent treatment discontinuation should be entered by the Investigator in the eCRF when considered as confirmed.

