9 ASSESSMENT OF INVESTIGATIONAL MEDICINAL PRODUCT

9.1 PRIMARY ENDPOINT

The primary endpoint for this study is the number (n) and percentage (%) of patients experiencing any TEAE (definition see [Section 10.4.1.1](#)) during total study periods.

Additional analyses will describe the number (n) and percentage (%) of patients experiencing any:

- Serious adverse events (SAE) (SAE definition refers to [Section 10.4.1.2](#)).
- Adverse events of special interest (AESI) (AESI definition refers to [Section 10.4.1.3](#)).
- Adverse events related to IMP.
- Adverse events leading to permanent IMP discontinuation.
- Adverse events other than ISR.

Adverse events, including SAEs and AESI, will be collected at any time during study starting from signed consent form. Any new AEs (including worsening AEs) and ongoing AEs (with onset date before the day of enrollment) at enrollment visit (when done on the same day of EOT or EOS of parent study) will be reported in present study. The Investigator will ask the patient and parents how he/she has felt since the last study visit. To assure the continuing safety of patients in this study, an independent DMC will be responsible for reviewing the safety data on a periodic basis throughout the course of the study as outlined in [Section 6.4](#).

The Investigator should take all appropriate measures to ensure the safety of the patients. Notably, he/she should follow up the outcome of SAEs/AESI until clinical recovery is complete and laboratory results have returned to normal or until progression has been stabilized or death. In all cases, this may imply that observations will continue beyond the last planned visit per protocol, and that additional investigations may be requested by the Sponsor.

When treatment is prematurely discontinued, the patient's observations will continue until the end of the study as defined by the protocol for that patient.

In case of any SAE/AESI with immediate notification brought to the attention of the Investigator at any time after the end of the study for the patient and considered by him/her to be caused by the investigational product with a reasonable possibility, this should be reported to the Sponsor.

Adverse events for each patient will be monitored and documented from the time the subject gives informed consent/assent at Visit 1 until the EOS visit, except for:

- Serious adverse events.
- Adverse events that are ongoing at database lock.

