10 STUDY PROCEDURES

The clinical trial consists of 3 periods, using an add-on therapy approach to conventional background asthma controller medications:

- Enrollment (Visit 1 of present study).
- Open-label treatment period (52 weeks; Visits 1-10).

During the open-label treatment period, patients will continue their background therapy dose regimen, as maintained in the parent study or as modified based on Investigator's judgement.

- Post-treatment period (12 weeks; Visit 11).

The study visits occur on the planned dates (relative to the first injection), as scheduled. The visit schedule should be adhered to within ± 3 days in the treatment period and ± 1 week for the remaining study period.

Spirometry should be done at the study site approximately the same time of the day (preferably in the morning, but it could be done at a different time of the day). Spirometry should be performed at visits as detailed in [Section 9.2.1.2](#).

Once every 2 weeks IMP administration must be separated by at least 11 days. Once every 4 weeks IMP administration must be separated by at least 25 days. The treatment period visits occur q2w up to Visit 3 (Week 4), q4w up to Visit 8 (Week 24), and approximately every 12-16 weeks up to the EOS visit as detailed in [Section 8.1.3](#).

Investigational medicinal product can be administrated at home from Visit 2 (Week 2) after approval of Investigator. Patients should be monitored for a minimum of 30 minutes after injections at home. Observations should be recorded in a support document by injection giver and provided to Investigator or delegated during onsite visit. However, if the parent(s)/caregiver(s)/legal guardian(s) or the Investigator decides not to administer IMP at home, the injections can be performed at the study site by way of unscheduled visits. Patients should be monitored at the study site for a minimum of 30 minutes after injections.

At the time of permanent treatment discontinuation, patients will perform the early treatment discontinuation (ETD) visits including early EOT visit and early EOS visit. Early EOT will be performed 2 weeks (with a ± 3 days window) after last IMP injection whenever possible. If the time of decision taken for permanent IMP discontinuation is >2 weeks after last IMP injection, this early EOT visit should be scheduled as early as possible from permanent discontinuation of IMP decision.

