11.4.3.1 Adverse events

The treatment-emergent period is defined for the two analysis sets separately as follows.

For the full analysis set, the treatment emergent period is from the date of first IMP injection to the date of the last IMP injection +14 weeks for the patients who end the dupilumab treatment on either 100 mg q2w or 200 mg q2w regimen; and, the treatment emergent period is from the date of first IMP injection to the date of the last IMP injection +16 weeks for the patients who end the dupilumab treatment on 300 mg q4w regimen.

For the modified analysis set, the treatment emergent period is from the date of first IMP injection to the date of the last IMP injection +14 weeks for the patients who never expose to the 300 mg q4w regimen; and, the treatment emergent period is from the date of first injection of 100 mg q2w regimen to the date before the first injection of the 300 mg q4w regimen for the patients who uptitrate the dosage from 100 mg q2w to 300 mg q4w during the study.

Adverse event reported in this study will be coded using the Medical Dictionary for Regulatory Activities (MedDRA) in effect at Sanofi at the time of database lock. Adverse events occurred during the treatment-emergent period will be considered as TEAEs.

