| | Residual treatment | Patients with last IMP on 100mg/200mg q2w regimen | Date of last IMP +15 days | Date of last IMP +14 days +12 weeks (84 days) |

| Analysis Set | Epoch | Applicable Patients | Epoch Start | Epoch End |
|------------------------------------------------------------------------------------------------------------------------------|--------------------|-------------------------------------------------------------|----------------------------------------------|-----------------------------------------------|
| | | Patients with last IMP on 300 mg q4w regimen | Date of last IMP +29 days | Date of last IMP +28 days +12 weeks (84 days) |
| | Post-treatment | All | Residual treatment Epoch End date +1 day | Open ended |
| Modified analysis set (not applicable to patients who initiate the treatment on 300 mg q4w regimen since Week 0 of LTS14424) | Screening | All | -- | The day before the date of first IMP |
| | Treatment | Patients on 100 mg/200 mg q2w regimen only | Date of the first IMP in LTS14424 | Date of last IMP +14 days |
| | | Patients who switched regimen from 100 mg q2w to 300 mg q4w | Date of the first IMP in LTS14424 | The date before the first dose of 300 mg q4w |
| | Residual treatment | Patients on 100 mg/200 mg q2w regimen only | Date of last IMP +15 days | Date of last IMP +14 days +12 weeks (84 days) |
| | | Patients who switched regimen from 100 mg q2w to 300 mg q4w | N/A | N/A |
| | Post-treatment | Patients on 100 mg/200 mg q2w regimen only | Residual treatment Epoch End date + 1 day | Open ended |
| | | Patients ever switch regimen from 100 mg q2w to 300 mg q4w | N/A | N/A |

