3 STATISTICAL ANALYSES

3.1 GENERAL CONSIDERATIONS

In general, continuous data will be summarized using the number, mean, standard deviation (SD), median, minimum, and maximum for observed data and the change from baseline. Categorical and ordinal data will be summarized using the count and percentage of participants.

The baseline values for efficacy, safety, PK, ADA and other endpoints are defined as the last available measurements prior to the first IMP dose if the participant is treated, or the last available value up to enrollment if the participant is not exposed to IMP.

Unless otherwise specified, all analyses will be performed on each dose regimen group and overall.

Observation period

The observation period will be divided into 4 segments:

- The **pre-treatment period** is defined as the period up to first IMP administration.
- The **treatment-emergent (TE) period** is defined as the period from the first IMP administration to the last IMP administration + 98 days for participants with IMP on 100 mg/200 mg q2w regimen, or to the last IMP administration + 112 days for participants on 300 mg q4w regimen. The treatment-emergent period includes the following 2 periods:
 - The **on-treatment period** is defined as the period from the first IMP administration to the last administration of the IMP + 14 days for participants with IMP on 100 mg/200 mg q2w regimen, or to the last administration of IMP + 28 days for participants on 300 mg q4w regimen.
 - The **residual treatment period** is defined as the period from the end of the on-treatment period to the end of the treatment-emergent period.
- The **post-treatment period** is defined as the period from the end of the treatment-emergent period.

The on-study observation period is defined as the time from start of intervention until the end of the study defined as the status date collected on e-CRF page “Completion of End of Study”.

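### When the early EOT is held 2 weeks after a last 300 mg q4w dose, the early EOS falls nominally 14 days before that regimen's 16-week treatment-emergent period ends

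*Protocol*

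**What the plan says.** **Early-stop visits.** Protocol Section 10 states "Early EOT will be performed 2 weeks" after the last injection, ±3 days, where possible. Section 10.3.4 has "Early EOT visit: 2 weeks (with a ± 3 days window) after last IMP injection" and then "Early EOS visit: 12 weeks after early EOT visit with a" ±1-week window. Section 17.7.2.9 repeats the scheme for Japan. None of the three has a version for 300 mg q4w. If the decision to stop comes later than this, Section 10.3.4 says "this early EOT visit should be scheduled as early as possible from permanent discontinuation of IMP decision", and the early EOS moves with it.

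**Treatment-emergent period.** Protocol Section 11.4.3.1 (full analysis set) runs the period from the first injection "to the date of the last IMP injection +16 weeks for the patients who end the dupilumab treatment on 300 mg q4w regimen", against 14 weeks for either q2w regimen. Section 17.7.2.10.4.3 says the same for Japan. Table 3 in Section 2 of the main SAP ends the q4w residual epoch at "Date of last IMP +28 days +12 weeks (84 days"). Section 3.1 of the Japan SAP runs the period "to the last IMP administration + 112 days for participants on 300 mg q4w regimen".

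**Adverse event collection.** Protocol Section 9.1 has events documented "from the time the subject gives informed consent/assent at Visit 1 until the EOS visit", with exceptions for serious events and for events still ongoing at database lock.

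**Other follow-up wording.** Section 10.3.4 opens by following early stoppers to the planned end of the study, or until an event under follow-up has recovered or stabilised, whichever is later. Footnote b of the Japan flow chart asks early stoppers to keep attending on the visit schedule until EOS.

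**The concern.** The early-stop timing fits a 2-week dosing interval: 2 weeks to EOT plus 12 weeks to EOS is exactly the q2w treatment-emergent period. For a child whose last dose was 300 mg q4w, the analysis counts events for 2 weeks longer than the early EOS nominally allows.

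The main-study primary endpoint is the number and percentage of patients with any treatment-emergent adverse event (TEAE). A new non-serious event between the early EOS and day 112 would count as treatment-emergent but might never be recorded. The EOS assessments, including the last laboratory, ADA and ECG checks, would also come before the period ends.

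In the Japan substudy, where TEAEs are a secondary endpoint, children of 30 kg or less are randomised 1:1 to 100 mg q2w or 300 mg q4w. Early stoppers in the two groups would be followed to different points relative to their own safety periods.

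**Working it through.** All days are counted from the last injection.

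**1. Reproduce the stated periods** (dose interval + 84 days, main SAP Table 3).
- q4w: 28 + 84 = 112 days = 16 weeks. This matches protocol 11.4.3.1 and the Japan SAP.
- q2w: 14 + 84 = 98 days = 14 weeks. This also matches.

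**2. Completers, nominally.** The Japan section puts the last dose at Week 50 for q2w and Week 48 for q4w. In the main study, the Week 48 call asks for 28 ± 3 days between the last q4w dose and EOT, which gives the same Week 48.
- q2w: Week 64 − Week 50 = 14 weeks.
- q4w: Week 64 − Week 48 = 16 weeks.

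Both reach the end of their period.

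**3. Early stoppers, standard route** (EOT at 14 ± 3 days, EOS 84 ± 7 days later).
- Nominal: 14 + 84 = day 98
- Earliest: 11 + 77 = day 88
- Latest: 17 + 91 = day 108

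Against day 112 the shortfall is 112 − 98 = 14 days nominally, with a range of 112 − 108 = 4 to 112 − 88 = 24 days. Nominally that is 14/112 = 12.5% of the post-dose period. No permitted use of the windows reaches day 112 on this route. Against the q2w end at day 98, the nominal shortfall is 0.

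**4. Late decision to stop** (EOS = EOT day + 84, window ±7).

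| Early EOT (day) | Nominal EOS (day) | EOS with window (day) | Nominal shortfall (days) |
|---|---|---|---|
| 18 | 102 | 95–109 | 10 |
| 21 | 105 | 98–112 | 7 |
| 24 | 108 | 101–115 | 4 |
| 28 | 112 | 105–119 | 0 |
| 35 | 119 | 112–126 | 0 |

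**5. If the planned-end sentence or Japan footnote b governs.** A q4w child who misses the Week 48 dose had the last dose at Week 44 or earlier, assuming doses stay on the 4-week grid. Week 64 − Week 44 = 20 weeks = 140 days, which is past day 112. Under that reading there is no gap.

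**The case against.** Four replies have force.

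- **Follow-up may run longer than the early EOS.** Section 10.3.4 opens with follow-up to the planned study end, and Japan footnote b points the same way. If those govern, day 112 is covered. But Section 10.3.4 then orders an early end-of-study visit with all the Visit 11 assessments and does not say how the two fit together. A site could reasonably follow either. This limits the claim to events that may be missed; it does not remove the conflict.
- **The gap does not affect every q4w early stopper.** A decision taken when the next dose is due, or after a missed dose, puts EOT at about day 28 or later and closes the nominal gap. With the +7-day window, an EOT on day 21 can already reach day 112. This stands.
- **The plan already tolerates some shortfall.** With windows, a q4w completer's EOS falls at (28 ± 3) + (84 ± 7) = day 102 to 122, up to 10 days short of 112. A q2w early stopper's falls at day 88 to 108, up to 10 days short of 98. This stands too. What is particular to q4w early stoppers is the 14-day nominal offset.
- **The possible loss is narrow.** Serious events are excepted from the EOS cut-off, related serious events are still reported after study end (Section 10.4.4), and existing events are followed to recovery or stabilisation. The endpoint is binary, so a missed event changes it only for a child with no earlier TEAE. The main SAP (Section 1.6) calls the number exposed to 300 mg q4w very limited, and its modified analysis set excludes data on or after the first q4w dose. Japan enrolled 13 children in all.

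**Conclusion.** The mismatch is real but limited. When early EOT is held at 2 weeks after a last 300 mg q4w dose, the early EOS comes nominally 14 days (4 to 24 with the windows) before the treatment-emergent period ends. New non-serious events in that tail may not be captured, and the final EOS samples precede its end. This assumes that the early EOS visit does end routine collection for that child, which the documents leave open.

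A reader might infer that the end of the safety period goes unobserved for all q4w early stoppers. The documents do not support that: the late-decision route and the competing follow-up sentences both cut against it. A reader might also infer that the children affected are mainly those stopped for safety. No counts of discontinuation reasons are given, Section 10.3.3 also lists patient request, sponsor request and protocol deviation, and a child stopped for a TEAE is already counted in the endpoint.

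The number of q4w early stoppers is not stated, so the effect on TEAE incidence cannot be computed. Given the limited q4w exposure, it is probably small in the main study. In Japan, with a minimum of 3 children per regimen, a single child could change a percentage visibly.

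**What to change.** Reconcile protocol Sections 10, 10.3.4 and 17.7.2.9, and Japan flow chart footnote b, with Sections 11.4.3.1 and 17.7.2.10.4.3 and both SAPs:

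- Time the early EOS from the last injection, by regimen, so that adverse event observation reaches the end of the treatment-emergent period the documents already define (16 weeks after a last q4w dose, 14 weeks after a last q2w dose).
- Leave the early EOT where it is. Moving both visits would delay the early EOT laboratory, ECG and ADA checks for no gain.
- State which follow-up sentence in Section 10.3.4 governs, and whether Japan footnote b overrides the early EOS.
- For visits already held, report how many q4w early stoppers were not observed to day 112, by study part.

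The cost is protocol wording, one count in each report, and an early EOS about 2 weeks later for q4w early stoppers. No visit or procedure is added. Keeping a ±1-week window around day 112 would still allow up to 7 days' shortfall, so the amendment should say whether that is accepted.

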10.3.5 Procedure and consequence for patient withdrawal from study

The patients may be withdrawn from the study at any time during the course of study if their parent(s)/caregiver(s)/legal guardian(s) decide to do so, and irrespective of the reason without any effect on their care. However, if patients no longer wish to take the IMP, they will be encouraged to remain in the study and perform the procedures planned for the EOT/EOS visit, including spirometry.

The Investigators should discuss with parent(s)/caregiver(s)/legal guardian(s) key visits the patient to attend. The value of all their study data collected during their continued involvement will be emphasized as important to the public health value of the study.

Patients who withdraw from the study treatment should be explicitly asked about the contribution of possible AEs to their decision and any AE information elicited must be documented.

All study withdrawals must be recorded by the Investigator in the appropriate screens of the eCRF and in the patient's medical records. In the medical record, at least the date of the withdrawal and the reason should be documented.

In addition, a patient may withdraw his/her consent to stop participating in the study. Withdrawal of consent for treatment should be distinguished from withdrawal of consent for follow-up visits and from withdrawal of consent for nonpatient contact follow-up, for example medical record checks. The site should document any case of withdrawal of consent.

For patients who fail to return to the site, unless the patient withdraws consent for follow-up, the Investigator must make the best effort to recontact the patient (for example contact patient's family or private physician, review available registries or health care databases), and to determine his/her health status, including at least his/her vital status. Attempts to contact such patients must be documented in the patient's records (for example times and dates of attempted telephone contact, receipt for sending a registered letter).

Patients who have withdrawn from the study cannot be re-enrolled (treated) in the study. Their inclusion and treatment numbers must not be reused.

10.4 OBLIGATION OF THE INVESTIGATOR REGARDING SAFETY REPORTING

10.4.1 Definitions of adverse events

10.4.1.1 Adverse event

An AE is any untoward medical occurrence in a patient or clinical investigation patient administered a pharmaceutical product and which does not necessarily have to have a causal relationship with this treatment.

Protocol-defined severe asthma exacerbation events (for detailed definitions see [Section 9.2.1.1](#)) are collected as efficacy endpoints on the e-CRF. Only asthma exacerbations which fulfill a seriousness criterion should be reported as an AE (SAE) (as per [Section 10.4.1.2](#)).

10.4.1.2 Serious adverse event

A SAE is any untoward medical occurrence that at any dose:

- Results in death, or,
- Is life-threatening, or,

Note: The term “life-threatening” in the definition of “serious” refers to an event in which the patient was at risk of death at the time of the event; it does not refer to an event which hypothetically might have caused death if it were more severe,

- Requires inpatient hospitalization or prolongation of existing hospitalization, or,
- Results in persistent or significant disability/incapacity, or,
- Is a congenital anomaly/birth defect,
- Is a medically important event,

Medical and scientific judgement should be exercised in deciding whether expedited reporting is appropriate in other situations, such as important medical events that may not be immediately life-threatening or result in death or hospitalization but may jeopardize the patient or may require medical or surgical intervention (that is specific measures or corrective treatment) to prevent one of the other outcomes listed in the definition above.

Note: The following list of medically important events is intended to serve as a guideline for determining which condition has to be considered a medically important event. The list is not intended to be exhaustive:

- Intensive treatment in an emergency room or at home for:
 - Allergic bronchospasm,
 - Blood dyscrasias (that is agranulocytosis, aplastic anemia, bone marrow aplasia, myelodysplasia, pancytopenia, etc.),
 - Convulsions (seizures, epilepsy, epileptic fit, absence, etc.)

- Development of drug dependence or drug abuse,
- Alanine aminotransferase (ALT) $>3 \times$ ULN + total bilirubin $>2 \times$ ULN or asymptomatic ALT increase $>10 \times$ ULN,
- New psychosis,
- Suicide attempt or any event suggestive of suicidality,
- Syncope, loss of consciousness (except if documented as a consequence of blood sampling),
- Bullous cutaneous eruptions,
- Bullous cutaneous eruptions requiring treatment,
- Cancers diagnosed during the study,
- Chronic neurodegenerative diseases (newly diagnosed).

